9.6 DATA MANAGEMENT

The data abstracted from eligible patients in this study will be recorded on the CRF or other applicable forms. The designated personnel will capture, check, store, and analyze the data. The designated personnel will follow Boehringer Ingelheim standard operating procedures (SOPs) and their own internal SOPs.

A data validation plan (DVP) will be created to describe the process for data validation.

Data will be transferred to Boehringer Ingelheim after the closure of the study.

9.7 DATA ANALYSIS

Statistical analyses will be conducted by the designated personnel. The main analysis population will consist of all eligible patients (i.e., all patients fulfilling all inclusion criteria and no exclusion criterion).

Descriptive analyses will be performed to summarize patient baseline characteristics, the observation period, the time to exacerbation/or to escalating to triple therapy, and the rates of exacerbation, etc. Continuous variables include number, mean, median, standard deviation (SD), range (minimum and maximum value), and 95% confidence intervals (CI). Categorical variables are frequency and percentage.

Statistical analysis of all data will be performed using the latest version of SAS® statistical software (SAS Institute, Cary, NC, USA) or other commercially available standard statistical software.

All information already collected as part of the study will be retained for further analyses; however, no extra efforts will be made to obtain or record additional information regarding the patient. In general, data imputation will not be permitted for any analyses in this study.

9.7.1 Main analysis

The propensity score matching approach* will be used to balance the baseline characteristics between the study cohorts. These data will be compared descriptively between patients receiving different regimens (Tio + Olo vs. other LABA/LAMA vs. LAMA). If the propensity score matching is done, the difference before and after matching will be considered both.

For the primary outcome

Time to the first moderate or severe COPD exacerbation will be compared between different cohorts using Kaplan-Meier curves with the incidence and time to events, and statistical significance will be assessed using log-rank tests.

Time to first acute exacerbation starts from the index date to the date of the first acute exacerbation recorded on the CRF. Patients with exacerbation free at the time of escalating to ICS or no documented with exacerbations will be censored.

For secondary outcomes

- Time to escalating to dual/triple therapy will also be analysed using Kaplan-Meier curves and log-rank tests.
- The annualized rate of exacerbation with various severity will be calculated for each study group (episodes/patient-year), and the differences between the three cohorts will be compared by rate ratio.
- Results of lung function (i.e., spirometry data) and COPD assessments (i.e., CAT and mMRC) will be evaluated by the change from baseline. Pair *t*-test or other applicable statistical methods will be used for assessing the intra-group difference under a significance level of 0.05.
- Chi-square test or Fisher's exact test will be applied for categorical variables such as reasons for switching/escalating therapies, frequency, and percentage, etc.

*NOTE: Variables may include but not limited to age, gender, disease duration before index date, smoking status, body mass index, COPD assessment score (e.g., CAT and mMRC), spirometry data (e.g., FEV₁), oxygen therapy, comorbidities, disease severity, previous exacerbation, previous treatments, or eosinophil counts, where appropriate.

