| Study design: | 
This is a retrospective, multi-center, cohort study to collect the data on COPD patients who were administered with LABA/LAMA (FDC or free combo) or LAMA treatment for 3 months at least prior to 30 June 2018. For LABA/LAMA therapy, new initiation or switching from other therapy (i.e., single/dual/triple) are both acceptable; for LAMA
 | | |

Proprietary confidential information © 2019 Boehringer Ingelheim International GmbH or one or more of its affiliated companies

| | |
|--------------------|---|
| | 
treatment, only new initiation will be acceptable. The data abstracted from eligible patients will be recorded only when they are available in the medical chart and will be categorized into the cohort A (patients treated with Tio + Olo), B (patients treated with other LABA/LAMA therapy), and C (LAMA therapy).
 
The follow-up period for each patient will be from the index date* until the date of death or 1 year after the index date, whichever occurs first. Patients will be censored at the time from one LAMA/LABA or LAMA switched to another LAMA/LABA or ICS.
 
*Index date: It is defined as the date of COPD patients in the cohort A and B starting using LABA/LAMA therapy regardless of new initiation or switching from other single/dual/triple treatment, or the date of the patients in the cohort C starting using LAMA treatment.
 |
| Population: | 
This study plans to review the medical chart from approximately 1,800 COPD patients receiving LABA/LAMA or LAMA treatment for 3 months at least prior to June 30 2018 in Taiwan.
 
Inclusion criteria
 
Patients who fulfil ALL the following criteria are included.
 
1. Patients who diagnosed with COPD who were prescribed with LABA/LAMA (FDC or free combo) as a new initiation or switching from other therapy (i.e., single/dual/triple), or newly receiving LAMA treatment for 3 months at least prior to 30 June 20182. Male or female patients ≥ 40 years of age 
Exclusion criteria
 
Patients who meet the following criterion are not included.
 
1. Patients with documented diagnosis of bronchial asthma, asthma-COPD overlap syndrome (ACOS), bronchiectasis, cystic fibrosis, or lung cancer |

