9. RESEARCH METHODS

9.1 STUDY DESIGN

It is a retrospective, multi-center, cohort study to collect the data on COPD patients who were administered with LABA/LAMA (FDC or free combo) or LAMA therapy for 3 months at least prior to 30 June 2018. The patients using LABA/LAMA therapy will be enrolled regardless of new initiation or switched from other single/dual/triple treatment, whereas those using LAMA treatment will only be acceptable when LAMA is newly initiated. This study aims to estimate the occurrence of COPD exacerbation in the COPD population under the real-world practice in Taiwan. Additionally, the study also assesses outcomes of clinical characteristics and prescription patterns for patients using LABA/LAMA or LAMA. After Institutional Review Board's (IRB) permission, it will be carried out in around 12 medical centers in Taiwan and plans to collect the clinical data abstracted from the medical charts of approximately 1,800 eligible patients. The eligible patients will be separated into three cohorts based on the prescription for COPD on the index date. Cohort A includes the patients treated with Tio + Olo, cohort B is the patients treated with other LABA/LAMA therapy, and cohort C is the patients receiving LAMA treatment. No investigational or interventional treatment will be provided in the retrospective study.

The retrospective study will review medical charts of COPD patients with LABA/LAMA or LAMA therapy until death or 1 year after the index date, whichever occurs first. The data collection will be conducted after eligibility assessment. Medical records will be reviewed and relevant information will be abstracted for various details such as patient demographics, diagnosis of COPD, smoking status, records of exacerbations and hospitalization, examinations of lung function and laboratory, treatments related to COPD or comorbidities, reasons for treatment switching, and comorbidities.

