9.3.2.2 Secondary outcomes

- Annualized rate of mild/moderate/severe exacerbation
- Time/reason (e.g., severe airflow limitation, diagnosis of asthma, worsening exacerbation) from LABA/LAMA escalating to LABA/LAMA/ICS or from LAMA to dual therapy

Proprietary confidential information © 2019 Boehringer Ingelheim International GmbH or one or more of its affiliated companies

- Percentage of patients receiving LABA/LAMA switched to triple therapy or LAMA switched to dual therapy
- Change in pulmonary function after LABA/LAMA or LAMA initiation
- Use of rescue medications

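### Event-free deaths are by implication censored in the Kaplan-Meier analyses of exacerbation and escalation, so the incidence read from the curves modestly overstates the share of patients affected

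*Combined protocol and SAP*

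**What the plan says.** The primary outcome is time to first moderate or severe exacerbation. Section 9.7.1 states that it "will be compared between different cohorts using Kaplan-Meier curves with the incidence and time to events", with a log-rank test. Among the secondary outcomes, "Time to escalating to dual/triple therapy will also be analysed using Kaplan-Meier curves and log-rank tests".

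Follow-up in section 9.1 runs "until death or 1 year after the index date, whichever occurs first", and the Abstract defines it in the same terms. The censoring rule in section 9.7.1 is: "Patients with exacerbation free at the time of escalating to ICS or no documented with exacerbations will be censored". The Abstract has a wider one: "Patients will be censored at the time from one LAMA/LABA or LAMA switched to another LAMA/LABA or ICS". Neither mentions death.

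Escalation is also a separate outcome in section 9.3.2.2, "Percentage of patients receiving LABA/LAMA switched to triple therapy or LAMA switched to dual therapy", and section 9.7.1 plans chi-square or Fisher's exact tests for categorical variables, percentages included. No denominator or follow-up rule is given for that percentage.

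**The concern.** Death ends follow-up and is not itself an event, and patients without a documented event are censored. A patient who dies event-free therefore has nowhere to go but the censored group. Kaplan-Meier assumes that a censored patient could still have the event later. That is untrue of the dead, so one minus Kaplan-Meier describes a hypothetical population in which nobody dies. It exceeds the share of real patients affected whenever anyone dies event-free.

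The primary objective is to describe how often exacerbations occur in routine practice, so the incidence is a headline result and not merely a by-product of the log-rank test. Escalation will in addition be reported in two ways, as a Kaplan-Meier curve and as a crude percentage, and nothing in the plan ensures that the two agree.

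**Working it through.** **Inputs from the plan.** Section 9.5 gives 0.78 and 0.90 events per patient-year. Their ratio, 0.78/0.90 = 0.867, agrees with the stated 0.87. The Table 2 confidence intervals concern the precision of that ratio and are not used here. The plan gives no expected 12-month incidence, mortality, escalation risk or switching rate, so it has no figure of its own to reproduce on this point.

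**Assumptions.** Hazards are constant over one year. The annualised rates are taken as the hazard *l* of a first event (Poisson). One-year mortality *d* is 2% to 15%, giving a death hazard *h* = −ln(1 − *d*).

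**Formulas.**
- Kaplan-Meier incidence with deaths censored: 1 − exp(−*l*).
- Cumulative incidence with death competing: *l*/(*l*+*h*) × [1 − exp(−(*l*+*h*))].
- No deaths in the first 3 months, same death hazard afterwards: [1 − exp(−0.25*l*)] + exp(−0.25*l*) × *l*/(*l*+*h*) × [1 − exp(−0.75(*l*+*h*))].

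The third formula covers a reading of the eligibility rule in which at least 3 months of treatment implies surviving them.

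**Exacerbation.** Kaplan-Meier gives 1 − exp(−0.78) = 54.2% and 1 − exp(−0.90) = 59.3%. Example at 0.78 and 5% mortality: *h* = 0.0513, and 0.78/0.8313 × [1 − exp(−0.8313)] = 0.938 × 0.565 = 53.0%.

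| Assumed mortality | Cum. incidence at 0.78 | KM excess (points) | Excess, no deaths in first 3 months | Cum. incidence at 0.90 | KM excess (points) | Excess, no deaths in first 3 months |
|---|---|---|---|---|---|---|
| 2% | 53.7% | 0.47 | 0.25 | 58.8% | 0.51 | 0.26 |
| 5% | 53.0% | 1.19 | 0.63 | 58.1% | 1.28 | 0.66 |
| 10% | 51.8% | 2.41 | 1.27 | 56.8% | 2.58 | 1.34 |
| 15% | 50.5% | 3.65 | 1.93 | 55.4% | 3.91 | 2.04 |

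**Difference between cohorts.** By Kaplan-Meier it is 59.34 − 54.16 = 5.18 points. With equal mortality it hardly moves: 5.18 − (1.28 − 1.19) = 5.09 at 5%, and 5.18 − (3.91 − 3.65) = 4.92 at 15%. With unequal mortality it does move. If 2% die in the 0.78 cohort and 10% in the 0.90 cohort, the difference is 5.18 − 2.58 + 0.47 = 3.07. With the mortalities reversed, it is 5.18 − 0.51 + 2.41 = 7.08.

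**Time to escalation.** Assume a one-year risk *p* of 10% to 30%, so *l* = −ln(1 − *p*) and Kaplan-Meier returns *p*. With mortality of 2% to 10%, cumulative incidence runs from 9.9% (*p* = 10%, mortality 2%) to 28.6% (*p* = 30%, mortality 10%). Kaplan-Meier is therefore 0.1 to 1.4 points too high.

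**Crude escalation percentage.** Everyone has a full potential year: index dates end on 30 June 2018 and data collection starts on 1 August 2019 (section 6). If death is the only early exit, the crude percentage equals the cumulative incidence. At *p* = 20% and 5% mortality both are 19.5%, against 20.0% by Kaplan-Meier. A gap arises only if patients who switch laterally or leave the chart stay in the denominator and their later escalations are not counted. At an assumed 10% of such exits the crude figure is 18.6%. Over assumed exits of 5% to 20%, with the risks and mortalities above, it is 0.2 to 2.9 points below the cumulative incidence.

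**The case against.** **The censoring of deaths is inferred, and section 9.7.2 is redacted.** Both are true. But the primary method and its censoring rule are set out in section 9.7.1, and they leave an event-free death no other treatment.

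**The effect is small.** This also stands. For 300 patients at 54%, the 95% margin is 1.96 × √(0.54 × 0.46/300) = 5.6 points, wider than any excess above. With equal mortality the cohort difference is almost unchanged, and the exacerbation rate per patient-year does not depend on Kaplan-Meier. However, the error always has the same sign, does not shrink with sample size, and falls on a headline figure.

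**The log-rank test.** A reader might infer that it is invalid. It is not: with deaths censored it compares cause-specific hazards, which is a legitimate comparison. If mortality differs, it simply need not match the difference in the shares of patients affected.

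**The crude escalation percentage.** A reader might infer that it is too low because patients who died stay in its denominator. They belong there: with death as the only early exit, the percentage is the cumulative incidence. A reader might also infer a spurious cohort difference from unequal follow-up. The documents give no switching or loss rates to support that. Many of the Abstract's switches are the escalation itself, namely ICS added to LABA/LAMA or LAMA moved to LABA/LAMA. Section 9.3.3.7 records treatments to one year or death, so escalations after a lateral switch can still be counted. What remains is that the plan does not say whether they are.

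**Conclusion.** The concern holds for the incidence read from the Kaplan-Meier curves. Event-free deaths are, by implication, treated as ordinary censoring, and the direction of the error is certain if anyone dies event-free. Its size rests on assumed mortality, constant hazards, and the use of annualised rates as first-event hazards. On those assumptions the excess is about 0.5 to 3.9 points for exacerbation (0.3 to 2.0 if no deaths are possible in the first three months) and 0.1 to 1.4 points for escalation.

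The comparison between cohorts is affected materially only if mortality differs between them, which cannot be ruled out in a non-randomised study. The crude escalation percentage is not biased by death; its fault is an undefined rule for lateral switches.

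**What to change.** - State in section 9.7.1 how event-free deaths are handled.
- Report 12-month Aalen-Johansen cumulative incidence with death as a competing event, with 95% confidence intervals, for the primary outcome and for time to escalation. Keep the log-rank test and label it as the comparison of cause-specific hazards.
- Keep the crude escalation percentage as a secondary outcome, on the same 12-month follow-up. State whether escalations after a lateral switch count. If they do, follow patients through the switch in both analyses. If not, treat the switch as a competing event in the cumulative incidence. Either way the two figures agree, apart from chart loss.
- Reconcile the censoring rules of the Abstract and section 9.7.1, and say that a switch which is itself the escalation is an event in that analysis.

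The cost is protocol or SAP wording and a standard software option. The follow-up definition already requires the date of death, and section 9.3.3.7 records prescription dates. Table 1 has no separate item for vital status, so confirm that the CRF captures the date of death. The downside is that reported incidences will be slightly lower.

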4. ABSTRACT

| | | | |
|---|--|---------------------------------|---|
| Name of company: Boehringer Ingelheim | | | |
| Name of finished medicinal product: Spiolto® (tiotropium/olodaterol) | | | |
| Name of active ingredient: tiotropium/olodaterol (ATC code: R03AL06; long-acting bronchodilators; a muscarinic receptor antagonist for tiotropium and a β adrenoreceptor agonist for olodaterol) | | | |
| Protocol date: 18 June 2019 | Study number: 1237-0086 | Version/Revision: 1.0 | Version/Revision date: 25 November 2019 |
| Title of study: | Taiwan Outcomes and Real-world Treatment Options for Chronic Obstructive Pulmonary Disease | | |
| Rationale and background: | 
Recently, more and more randomized controlled trials (RCT) demonstrated effectiveness of dual bronchodilators for the treatment of chronic obstructive pulmonary disease (COPD). DYNAGITO trial¹ has provided further evidences for tiotropium + olodaterol (Tio + Olo) compared with tiotropium in reducing moderate/severe exacerbations. In the real-world setting in Taiwan, the medication environment and electronic medical charts are well-established in medical centers. Hence, retrospective analysis is fully possible. Boehringer Ingelheim (BI) Taiwan and clinical practitioners' common goal are to adopt optimal treatment for COPD patients diagnosed per GOLD guideline.
 
So far, we can refer to some head to head studies examining the impact on lung function of various LABA/LAMA combinations; however, there is no study observing real world outcomes on prevention/risk reduction of acute exacerbations in Taiwan. The extent of outcomes from Tio + Olo (Spiolto®), other LABA/LAMA fixed-dose combinations [FDC]/free combos, or LAMA treatment of benefit for COPD patients in reducing acute exacerbation, is of great interest to explore.
 | | |
| Research question and objectives: | 
The primary objective is to understand the occurrence of COPD exacerbations in patients treated with LABA/LAMA or LAMA in the routine clinical practice in Taiwan.
 
The secondary objectives are to realize the clinical characteristics and prescription patterns for the COPD population in Taiwan.
 | | |

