| Data analysis: | A Data Validation Plan (DVP) will be prepared to describe the processes for data validation. The data abstracted from the medical chart will be described with number, mean, standard deviation (SD), range, and 95% confidence intervals (95% CI) for continuous variables, and frequencies and percentages for categorical variables. |

Proprietary confidential information © 2019 Boehringer Ingelheim International GmbH or one or more of its affiliated companies

| | |
|--------------------|--|
| | 
The propensity score matching approach* will be used to balance the baseline characteristics between the study cohorts (Tio + Olo vs. other LABA/LAMA vs. LAMA therapy).
 
These data will be compared descriptively between patients receiving different regimens (Tio + Olo vs. other LABA/LAMA vs. LAMA therapy). If the propensity score matching is done, the difference before and after matching will be considered both.
 
The annualized rate of exacerbation with various severities will be calculated for each study group (episodes/patient-year), and the differences between the three cohorts will be compared by rate ratio.
 
Time to the first moderate or severe COPD exacerbation or escalating to dual or triple therapy will be compared between different cohorts using Kaplan-Meier curves with the incidence and time to events, and statistical significance will be assessed using log-rank tests.
 
Chi-square test or Fisher's exact test will be applied for categorical variables such as reasons for switching/escalating therapies, frequency, and percentage, etc.
 
*NOTE: Variables may include but not limited to age, gender, disease duration before index date, smoking status, body mass index, COPD assessment score (e.g., CAT and mMRC), spirometry data (e.g., FEV₁), oxygen therapy, comorbidities, disease severity, previous exacerbation, previous treatments, or eosinophil counts, where appropriate.
 |
| Milestones: | 
Planned the start of data collection: July 2019
 
Planned the end of data collection: November 2019
 
Planned final study report: the end of January 2020
 |

Proprietary confidential information © 2019 Boehringer Ingelheim International GmbH or one or more of its affiliated companies

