9.3.2 Outcomes

9.3.2.1 Primary outcomes

- Time to the first moderate or severe COPD exacerbation

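### The visible main analysis gives no between-cohort effect estimate with a confidence interval for the primary outcome, and does not say which contrast or which analysis set leads

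*Combined protocol and SAP*

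**What the plan says.** The primary outcome in section 9.3.2.1 is "Time to the first moderate or severe COPD exacerbation". Section 9.7.1 says it will be "compared between different cohorts using Kaplan-Meier curves with the incidence and time to events", and that "statistical significance will be assessed using log-rank tests". The data analysis part of the abstract repeats this.

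On confounding, section 9.7.1 says "The propensity score matching approach* will be used to balance the baseline characteristics between the study cohorts". It then makes the matching conditional and does not rank the results: "If the propensity score matching is done, the difference before and after matching will be considered both". Section 9.7 states "The main analysis population will consist of all eligible patients". The cohorts are listed together as "Tio + Olo vs. other LABA/LAMA vs. LAMA".

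The only between-cohort effect measure in 9.7.1 is a rate ratio, and it applies to the annualized exacerbation rate, a secondary outcome. A 0.05 level is given only for within-group change from baseline.

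**The concern.** The rationale in the abstract says the study is meant to explore "The extent of outcomes from Tio + Olo" and of the alternatives. That calls for an estimate of how far the cohorts differ and how uncertain the difference is. For the primary outcome, the visible plan gives a curve and an incidence for each cohort plus a test, but no measure of the difference between cohorts with an interval.

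Two further choices are left open: which pair of cohorts is the main comparison, and whether the crude or the matched result is the primary one. The second matters most. Allocation was not randomised, cohorts A and B admit patients switching from other therapy, and cohort C admits only new initiators. Section 9.7.3 bars imputation, so patients without CAT, spirometry or eosinophil values may be lost from matching if those covariates are used. Crude and matched answers could well differ, and an unadjusted log-rank p-value in all eligible patients could be reported as the primary result without departing from the plan.

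**Working it through.** **1. Planning against analysis**

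- Contrast: section 9.5 and every row of Table 2 compare Tio + Olo with other therapy. Section 9.7.1 lists three cohorts and names no main pair.
- Measure: section 9.5 plans a ratio with a 95% CI. For the primary outcome, 9.7.1 gives Kaplan-Meier curves and log-rank tests.
- Population: section 9.7 makes all eligible patients the main population. Section 9.7.1 considers results before and after matching, with no order between them.

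**2. The plan's own figure**

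Table 2, row 1, gives a rate ratio of 0.87 (0.768, 0.978) for 0.78 against 0.90 per patient-year, 300 against 800 patients, at about 2 patient-years each. With a Poisson log rate ratio, SE = sqrt(1/(r1 × n1 × T) + 1/(r2 × n2 × T)):

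- T = 2: sqrt(1/468 + 1/1440) = 0.0532, giving 0.867 (0.781, 0.962).
- T = 1.5: sqrt(1/351 + 1/1080) = 0.0614, giving 0.867 (0.768, 0.978), the printed interval.
- T = 1, the longest follow-up allowed: sqrt(1/234 + 1/720) = 0.0752, giving 0.867 (0.748, 1.004).

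The mismatch between 2 and 1.5 patient-years is a separate matter, and nothing here depends on it. The table concerns the event rate. The plan states no event count, hazard ratio or power for the time-to-event outcome.

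**3. What the missing estimate would show (illustration)**

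Assume constant hazards equal to 0.78 and 0.90 and one year of follow-up for everyone. Expected first events are n × (1 − exp(−rate)).

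- 300 vs 800: 300 × (1 − exp(−0.78)) = 162 and 800 × (1 − exp(−0.90)) = 475. SE = sqrt(1/162 + 1/475) = 0.091. HR 0.87 (0.73, 1.04). By Schoenfeld's formula, sqrt(637 × 0.273 × 0.727) × |ln 0.867| − 1.96 = −0.35, so two-sided 5% power is about 36%.
- 300 vs 300 (1:1 matched, pairing ignored): 162 and 178 events, SE = 0.108, HR 0.87 (0.70, 1.07), power about 26%.
- With half a year of follow-up, power falls to 24% and 17.5% respectively.

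At this effect, 80% power needs about 1,933 events at 300:800 or 1,534 at 1:1.

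**4. Multiplicity**

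Take three pairwise tests at 0.05 with cohort sizes 300, 800 and 700, the last assumed as 1,800 − 1,100. Simulating the correlated contrasts gives a chance of at least one false positive of about 12%. This applies only if pairwise tests are run. The plan does not say whether they are, or whether one three-group test is used.

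**5. Matched pairs**

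In a simulation of 300 pairs with a shared within-pair frailty (SD 0, 0.5, 1.0; 4,000 runs each), the ordinary log-rank rejected a true null in 4.7%, 3.8% and 2.0% of runs. The pair-stratified test stayed near 5%. At HR 0.867, power was 27%, 20% and 11% for the ordinary test and 20%, 18% and 16% for the stratified one.

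**The case against.** The stated primary objective is descriptive: to understand how often exacerbations occur. Kaplan-Meier output with incidence and timing for each cohort serves that aim, and section 9.7 adds descriptive summaries. The secondary rate ratio gives a between-cohort measure for a closely related endpoint. Section 9.5 shows which contrast the sponsor had in mind. Matching, if done, adjusts by design. Section 9.7.2 is redacted in the table of contents and absent from the text, so a regression analysis could sit there.

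Most of this limits the point without removing it. It would be wrong to read the plan as giving p-values and nothing else, as having no contrast in view at all, or as provably lacking any model. But the plan does set significance tests between cohorts, and section 9.9 expects matching to make significant differences easier to observe. A rate ratio for a secondary outcome does not supply an estimate for the primary one.

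A reader might also count three contrasts, before and after matching, as six independent tests and quote 1 − 0.95^6 = 26.5%. The documents do not support that figure. They never specify six pairwise tests. Contrasts that share a cohort, and matched patients drawn from the unmatched ones, cannot be independent. Crude contrasts are also confounded, so their error rate need not be 5%.

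**Conclusion.** The point stands for the visible main analysis. The primary outcome has no between-cohort estimate with a CI, the contrast used for sizing is not carried into 9.7.1, and no rule says whether the crude or the matched result leads. The main consequence is that a confounded p-value could be presented as the primary finding. The illustration adds that, at the planning rates, power of about 26% to 36% makes a non-significant log-rank the likelier result even if the assumed effect is real; without an interval, the reader could not tell that from no difference. Those figures rest on constant hazards equal to the section 9.5 rates and a full year of follow-up.

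The multiplicity component is about 12% at most for three pairwise tests in one analysis set, under the assumed sizes. The matched-set component is minor. A reader might infer that ignoring matching inflates false positives, but the simulation shows the opposite for 1:1 pairs: a conservative test, incorrect standard errors and possibly lost power. Matching with replacement or at variable ratios could behave differently, and the plan specifies neither.

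**What to change.** In section 9.7.1 and the abstract, make the primary estimate a Cox hazard ratio with 95% CI for Tio + Olo versus other LABA/LAMA in the propensity-matched set. Use robust variance clustered on matched set, and adjust for covariates whose imbalance after matching exceeds a threshold stated in advance, for example an absolute standardised difference above 0.1. The threshold matters: adjusting for whatever looks imbalanced would be a post hoc choice.

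Amend section 9.7 so that the matched analysis leads. Treat the other contrasts and the unmatched results as supportive, and keep Kaplan-Meier and log-rank as description.

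The cost is one model per contrast on data already being collected, a proportional-hazards check, and a matching scheme written down first, since clustering needs defined sets. The matched sample is smaller, so the interval is wider: in the illustration, 0.70 to 1.07 rather than 0.73 to 1.04.
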